2.8.2 Deaths

Patient deaths will be summarized by primary SOC, PT and treatment phase (see Section 2.1.1 for treatment phase definitions). A patient listing of all deaths with primary and contributing reasons for death will be provided. All patients in the FAS will be included for the above analysis. Deaths will be coded using MedDRA terminology (v19.0 or later).

2.8.3 Laboratory data

Laboratory values will be summarized using shift tables (from baseline to most extreme post baseline value) by each laboratory parameter at its worst severity by treatment phase (see Section 2.1.1 for treatment phase definitions). The number and percentage of patients with

laboratory values will be presented by low/normal/high (low and high) classifications to compare baseline to worst post baseline value.

In addition, laboratory values and the change from baseline for each parameter by visit will be summarized by treatment group for both the randomized treatment and open-label extension phases. In the event there are multiple laboratory values within a visit, the worst value will be summarized.

A separate summary table will be presented by treatment phase (see Section 2.2.1 for treatment phase definitions) with the number and percentage of patients having notable lab abnormalities based on percent change from baseline (see Section 5.3 for a list of notable laboratory abnormalities).

Listings of all laboratory values will be provided. A separate listing for pregnancy tests will also be provided. Any notable laboratory abnormalities will be flagged.

2.8.4 Other safety data

2.8.4.1 Vital signs

All vital signs (systolic and diastolic blood pressure [mmHg], pulse rate [beats per minute {bpm}], respiration rate [breaths per minute], weight [kg], height [cm], and BMI [kg/m²]) will be descriptively summarized at each visit by treatment group for both the randomized treatment and open-label extension phases. Change from baseline will also be presented. Note that height is only collected at Visit 1.

A separate summary table will be presented with the number and percentage of patients having notable vital signs based on changes relative to baseline values (see Section 5.4 for a list of notable vital signs) by treatment phase (see Section 2.1.1 for treatment phase definitions).

2.8.4.2 Heart Failure (HF) Signs and Symptoms

The number and percentage of patients in the following HF signs and symptoms categories will be summarized by visit and treatment group for both the randomized treatment and open-label extension phases:

- Paroxysmal nocturnal dyspnea (Absent, Present)
- Fatigue (Absent, Present)
- Edema (Absent, Trace, Feet and Ankles, Lower Legs or Thighs, Sacrum)
- Peripheral edema (Absent, Present)
- Dyspnea at rest (Absent, Present)
- Dyspnea at upon effort (Absent, Present)
- Orthopnea (Absent, Present)
- Rales (Absent, Basilar only, >1/3 of lung filled)
- Jugular venous distention (Absent, Present)

- Presence of a third heart sound (Absent, Present)
- NYHA classification (Class I, Class II, Class III, Class IV)

2.8.4.3 Angioedema

The number and percentage of patients for categorical variables and summary statistics for continuous variables for the following angioedema assessment data will be presented by study phase and treatment group for both the randomized treatment and open-label extension phases.

- Outcome (Not recovered/Not resolved, Recovered/Resolved, Recovering/Resolving, Recovered/Resolved with Sequelae, Fatal, Unknown)
 - Duration of angioedema in days [*end date – start date + 1*]
- Timing of event (After first dose, after multiple doses, dose not given) [not asked for events that occurred during Screening study phase]
 - Study medication discontinued due to event (No, Yes, Unknown)
 - Event occurred within 1 day of dosing (Within 1 day of dose but less than or equal to 1 hour, Within 1 day of dose but greater than 1 hour, After 1 day of dosing, Unknown)
- History of prior angioedema or angioedema like event (No, Yes, Unknown)
- Medications taken at time of previous event
 - ACE inhibitor (No, Yes, Unknown)
 - ARB (No, Yes, Unknown)
 - Renin inhibitor (No, Yes, Unknown)
 - Other medications (No, Yes, Unknown)
- Presence of hereditary angioedema (No, Yes, Unknown)
- Any family members with history of angioedema-like events (No, Yes, Unknown)
- Signs and symptoms for current event
 - Shortness of breath/dyspnea (No, Yes, Unknown)
 - Difficulty swallowing/dysphagia (No, Yes, Unknown)
 - Difficulty speaking/dysarthria (No, Yes, Unknown)
 - Pain on swallowing/odynophagia (No, Yes, Unknown)
 - Stridor (No, Yes, Unknown)
 - Abdominal pain (No, Yes, Unknown)
 - Other (No, Yes, Unknown)
- Edema present (No, Yes)
 - Periorbital edema (No, Yes, Unknown)

- Head edema (No, Yes, Unknown)
 - Neck edema (No, Yes, Unknown)
 - Lip edema (No, Yes, Unknown)
 - Tongue edema (No, Yes, Unknown)
 - Throat edema (No, Yes, Unknown)
 - Submandibular edema (No, Yes, Unknown)
 - Genitalia edema (No, Yes, Unknown)
 - Extremities edema (No, Yes, Unknown)
 - Other (No, Yes, Unknown)
- Previous edematous episodes (No, Yes, Unknown)
 - Number of previous edematous episodes
- ACEi taken in the past (before screening) (No, Yes, Unknown)
- ACEi taken (other than study medication) during trial participation after screening (No, Yes, Unknown)
 - Dose changed within 2 days of event (No, Yes, Unknown)
- ARB taken in the past (before screening) (No, Yes, Unknown)
- ARB taken (other than study medication) during trial participation after screening (No, Yes, Unknown)
 - Dose changed within 2 days of event (No, Yes, Unknown)
- Patient suffering from influenza, common cold or upper respiratory tract infection at time of event (No, Yes, Unknown)
- Medication allergies (No, Yes, Unknown)
- Food allergies (No, Yes, Unknown)
- Potential causes of angioedema-like event
 - Food (No, Yes, Unknown)
 - Insect bite (No, Yes, Unknown)
 - Animal exposure (No, Yes, Unknown)
 - Medication (No, Yes, Unknown)
 - Dental work (No, Yes, Unknown)
 - Pollen (No, Yes, Unknown)
 - Dust (No, Yes, Unknown)
 - Concomitant disease (No, Yes, Unknown)

- Idiopathic (No, Yes, Unknown)
 - Other (No, Yes, Unknown)
- Medical intervention (No, Yes)
 - Administration of H-1 blocker (No, Yes)
 - Administration of H-2 blocker (No, Yes)
 - Administration of steroids (No, Yes)
 - Administration of epinephrine (No, Yes)
 - Admission to hospital (No, Yes)
 - Admission to ER (No, Yes)
 - Endotracheal intubation (No, Yes)
 - Tracheostomy (No, Yes)
 - Discontinuation of ACE inhibitor (other than study medication) (No, Yes)
 - Discontinuation of ARB (other than study medication) (No, Yes)
 - Other (No, Yes)

[figure not shown]
All angioedema assessment data will be listed. Additionally, the adjudicated assessment of the event will be listed separately.

[figure not shown]
2.9 Pharmacokinetic endpoints

Not applicable.

2.10 PD and PK/PD analyses

[figure not shown]
Not applicable.

[figure not shown]

[figure not shown]

2.12 Biomarkers

Not applicable.

2.14 Interim analysis

No interim analysis is planned.

3 Sample size calculation

[figure not shown]
Primary endpoint:

Assuming a significance level of 0.05, a total sample size of 136 patients would provide 90% power to detect a difference of 5000 in the change from baseline in mean activity counts collected during the most active 30 minutes between the sacubitril/valsartan treatment group and the enalapril group during Week 8, assuming a common standard deviation of 7400 (Maurer 2009) and a 20% drop-out rate and a 10% rate of patients with non-evaluable data. The assumed effect size of 68% (5000/7400) will be maintained in the event the log transformation is needed for the primary analysis thus not affecting the sample size calculation and power of the study.

Secondary endpoint:

Assuming a significance level of 0.05, a sample size of 136 patients would provide 93% power to detect a 3.5 point difference in the change from baseline in mean activity value during the sleep (expressed as counts per minute) between the sacubitril/valsartan treatment group and the enalapril group during Week 8, assuming a common standard deviation of 4.9 and a 20% drop-out rate and a 10% rate of patients with non-evaluable data (Peterson 2012).

4 Change to protocol specified analyses

5 Appendix

5.1 Imputation rules

5.1.1 Study treatment

Full dates for study treatment collected on the eCRF are required; therefore, no imputations will be made.

5.1.2 AE date imputation

The following algorithm should be used to estimate start dates for which only partial information is known:

- Missing day and month
 - If the year is the same as the year of first study treatment, then the day and month of the start date of treatment will be assigned to the missing fields.
 - If the year is prior to the year of first study treatment, then December 31 will be assigned to the missing fields.
 - If the year is after the year of first study treatment, then January 1 will be assigned to the missing fields.
- Missing month only
 - Treat day as missing and replace both month and day according to the above procedure.
- Missing day only
 - If the month and year are the same as the year and month of first study treatment, then the start date of treatment will be assigned to the missing day.
 - If the month and year are before the year and month of first study treatment, then the last day of the month will be assigned to the missing day.
 - If the month and year are after the year and month of first study treatment, then the first day of the month will be assigned to the missing day.

If the imputed start date result is after the stop date (and the stop date is complete), the imputed start date will be reset to the stop date.

The following algorithm should be used to estimate stop dates for which only partial information is known:

- Missing year
 - Date left missing.
- Missing month
 - Impute 'December'.
- Missing day
 - Impute 'last date of that month'.

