For summarization of adverse events [AEs], medications, protocol deviations, and notable vital signs and laboratory abnormalities by treatment phase, an assessment during the randomized treatment phase is defined as any assessment obtained in the following time interval:

Date of randomization (or date of first administration of study treatment, as appropriate) through the date of the Week 8 visit, inclusive.

Open-label extension phase

Assessments performed at Weeks 10, 12, or 16 (e.g., vital signs) are assigned to the open-label extension phase for summarization purposes. Unscheduled assessments are not assigned to a study phase.

For summarization of AEs, medications, protocol deviations, and notable vital signs and laboratory abnormalities by treatment phase, an assessment during the open-label extension phase is defined as any assessment obtained in the following time interval:

After the date of the Week 8 visit.

Last contact

The date of last contact will be the last visit date for each patient and will be derived by examining all visit data collected in the eCRFs.

Year, month and week

For reporting purposes, the rules below will be followed to convert a year, month and week to days.

1 year = 365.25 days

1 month = 30.3475 days

1 week = 7 days

1 day = 24 hours

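### Partial AE start dates are imputed without regard to the Week 8 switch, so some open-label events in both arms are counted in the randomized phase and none move back

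*SAP*

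**What the plan says.** SAP 5.1.2 has these start-date branches, all defined relative to first study treatment:

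- Day missing, month before first treatment: "then the last day of the month will be assigned to the missing day".
- Day missing, same month as first treatment: "then the start date of treatment will be assigned to the missing day".
- Day missing, later month: "then the first day of the month will be assigned to the missing day".
- Day and month missing, earlier year: "then December 31 will be assigned to the missing fields".
- Day and month missing, same year as first treatment: "then the day and month of the start date of treatment will be assigned to the missing fields".
- Day and month missing, later year: "then January 1 will be assigned to the missing fields".
- If the result falls after a complete stop date, "the imputed start date will be reset to the stop date".

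SAP 5.1.3 repeats the start-date rules for medications. No branch mentions the Week 8 visit or the first open-label dose, although SAP 2.1.1 defines the latter.

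For AEs and medications, SAP 2.1.1 sets the randomized phase as "Date of randomization (or date of first administration of study treatment, as appropriate) through the date of the Week 8 visit, inclusive"; everything after that visit is open-label. SAP 2.8.1.2 summarizes treatment-emergent AEs by these phases. SAP 1.1 puts all patients on sacubitril/valsartan in the open-label phase.

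**The concern.** The rule suits one question: did the event start on or after first treatment? The SAP then uses the same imputed date for a second question, namely the phase to which the event belongs. An open-label event can be dated back across the Week 8 visit.

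In the sacubitril/valsartan arm such an event has the wrong phase but the right drug. In the enalapril arm it began after the Week 8 visit, during the washout or on open-label sacubitril/valsartan, yet it falls in the enalapril period. Protocol 9.5.2 rests the safety assessment mainly on frequencies of AEs, SAEs and laboratory abnormalities, so the phase split of the AE tables matters to how the trial's safety is read.

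**Working it through.** The plan states no figure on this point, so there is nothing to reproduce.

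**Inputs.** Week 8 visit on Day 56 and end of open-label on Day 112 (Protocol Table 6-1); visit window of 3 days either side, so Day 53 to 59 (Protocol 6).

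**Assumptions.** First dose on Day 1; first-dose dates spread evenly over the calendar; onsets spread evenly from the day after the Week 8 visit to Day 112.

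**1. Direction.** Let f be the first-dose date and e the true onset, with e on or after f. The four branches that can apply return f, the 1st of e's month, f, or 1 January of e's year. None is later than e. An onset on or before the Week 8 visit therefore stays there, and the reverse shift is 0%. The stop-date reset cannot offset this, because it only moves a start earlier.

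**2. Day missing.** An open-label event moves exactly when it falls in the calendar month of the Week 8 visit.

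- In a month of L days, the mean number of days left after an evenly placed visit is (L − 1)/2.
- Over a 365-day year: (7×31×30/2 + 4×30×29/2 + 28×27/2)/365 = (3255 + 1740 + 378)/365 = 14.72 days.
- Share moved, visit on Day 56: 14.72/(112 − 56) = 26%.
- Visit on Day 53: 14.72/59 = 25%. Visit on Day 59: 14.72/53 = 28%.
- If onsets are counted only from the second day after the visit, enumeration gives 25% for Day 56 and 24% to 26% across the window.

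**3. Day and month missing.** An event in the year of first dose moves to the first-dose date. An event in the next year moves to 1 January, which is still in the randomized phase if the Week 8 visit is also in that year. It stays open-label only if the year end falls between the visit and the onset.

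- Open-label onsets are 56 to 111 days after Day 1, mean 83.5; the visit is 55 days after.
- In the year of first dose: 1 − 83.5/365 = 77%.
- Next year, with the visit in that year too: 55/365 = 15%.
- Share moved: 1 − (83.5 − 55)/365 = 92%. Across visit Days 53 to 59 it is 1 − 30/365 to 1 − 27/365, again 92% to 93%.

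Enumerating every first-dose date over four calendar years gives 26.3% and 92.2%, with no reverse moves.

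**4. Example.** First dose 10 January 2018, Week 8 visit 6 March 2018.

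| True onset | Day missing | Day and month missing |
|---|---|---|
| 20 March | 1 March, randomized | 10 January, randomized |
| 10 April | 1 April, open-label | 10 January, randomized |

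**5. Count.** Let p be the share of open-label AEs with a partial date and m the share of those that also lack the month. Misplaced events per 100 open-label AEs = 100 × p × [0.26(1 − m) + 0.92m]. The documents give neither p nor m. As m runs from 0 to 1:

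- p = 2% (assumed): 0.5 to 1.8
- p = 5% (assumed): 1.3 to 4.6
- p = 10% (assumed): 2.6 to 9.2

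**The case against.** Several points on the other side stand.

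- A reader might infer that partial dates always go to the earliest possible date. They do not: months or years before first treatment get the latest date, and the month or year of first treatment gets the first-dose date. With only the day missing, about three quarters of open-label events stay where they belong.
- A reader might also infer that the rule raises enalapril's AE rates relative to sacubitril/valsartan. The documents do not support that. The same shift inflates randomized-phase counts in both arms, and the net difference depends on each arm's open-label AE rate and partial-date rate, which are not given.
- That the event is tabulated under enalapril is a strong inference, not stated text: SAP 2.8.1.2 names the phases but not the table columns, and the table shells are a separate document.
- The AE tables are not the only randomized safety data. Laboratory values, vital signs and heart failure signs are summarized by visit and treatment group (SAP 2.8.3, 2.8.4) and do not depend on this rule. All safety analysis is descriptive, and all AEs are listed.
- Unknown months should be rare. AEs are sought at every visit (Protocol 7.1), open-label contacts are one to two weeks apart (Table 6-1), and incomplete entries are queried (Protocol 8.2, 8.3).

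These limit the size and the interpretation. They do not remove the mechanism: the phase tables use a date rule that does not recognize the phase boundary.

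**Conclusion.** The point holds as a minor defect. For onsets after first treatment, the rule moves about a quarter of day-missing open-label events (24% to 28%) and about 92% of those lacking day and month into the randomized phase, in both arms, with no movement back. In the enalapril arm the drug period is wrong as well. These shares assume even spread of first-dose dates and onsets. The number of events is unknown and probably small, and no direction of bias between the arms can be claimed.

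**What to change.** Keep the present rule for deciding treatment-emergent status. Add to SAP 5.1.2, and to 5.1.3 for medication start dates:

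- When a partial start date is compatible with both phases, the phase is set by the visit at which the record was first reported.
- If it was first reported after the Week 8 visit, and not at it, assign the open-label phase. Impute the latest of the day after the Week 8 visit, the first day of the known month and, when the month is also missing, 1 January of the known year, capped at the stop date.
- Otherwise keep the present rule.
- List the affected records. Where the reporting visit is not available, show a sensitivity table under the alternative assignment.

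The reporting visit is needed because a date rule alone only moves the error. Assigning the first open-label dose date whenever the month matches (taken as two days after the visit) nearly eliminates the present shift, but sends about 25% (23% to 27%) of randomized-phase day-missing events into the open-label phase.

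The cost is a short SAP insertion and a small amount of programming. Protocol 7.1 does not list the reporting visit among the AE form items, so it may have to be recovered from entry records. Events reported late will still sometimes be misplaced.

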5.1.3 Concomitant medication date imputation

The following algorithm should be used to estimate start dates for which only partial information is known:

- Missing day and month
 - If the year is the same as the year of first study treatment, then the day and month of the start date of treatment will be assigned to the missing fields.
 - If the year is prior to the year of first study treatment, then December 31 will be assigned to the missing fields.

- If the year is after the year of first study treatment, then January 1 will be assigned to the missing fields.
- Missing month only
 - Treat day as missing and replace both month and day according to the above procedure.
- Missing day only
 - If the month and year are the same as the year and month of first study treatment, then the start date of treatment will be assigned to the missing day.
 - If the month and year are before the year and month of first study treatment, then the last day of the month will be assigned to the missing day.
 - If the month and year are after the year and month of first study treatment, then the first day of the month will be assigned to the missing day.

If the imputed start date result is after the stop date (and the stop date is complete), the imputed start date will be reset to the stop date.

The following algorithm should be used to estimate stop dates for which only partial information is known:

- Missing year
 - Date left missing. Consider the medication to have been received at all periods after that period determined by the start date.
- Missing month
 - Impute 'December'.
- Missing day
 - Impute 'last date of that month'.

5.2 AEs coding/grading

The UBC coding team will code the AE terms using MedDRA v19.0 or later. If any terms are not coded, the data management team will issue queries to sites to update the AE term appropriately.

5.3 Laboratory parameters derivations

5.3.1 Laboratory grading

The collected laboratory values will be summarized by severity (low/normal/high) and not converted to Common Terminology Criteria for Adverse Events (CTCAE) grades.

5.3.2 Notable laboratory values

Hematology

Red blood cell (RBC) count >50% increase, >20% decrease

Hemoglobin	>50% increase, >20% decrease
Hematocrit	>50% increase, >20% decrease
White blood cell (WBC) count	>50% increase, >50% decrease
Platelet count	>75% increase, >50% decrease

Blood Chemistry

Alanine aminotransferase (ALT) (SGPT)	>150% increase
Aspartate aminotransferase (AST) (SGOT)	>150% increase
Blood urea nitrogen (BUN)	>50% increase
Creatinine	>50% increase
Total bilirubin	>100% increase
Alkaline phosphatase	>100% increase
Potassium	>20% increase, >20% decrease
Chloride	>10% increase, >10% decrease
Calcium	>10% increase, >10% decrease
Uric acid	>50% increase

5.4 Vital signs

5.4.1 Notable vital sign values

Systolic blood pressure	<90 mmHg and decrease of >20 mmHg from baseline
	>180 mmHg and increase of >20 mmHg from baseline
Diastolic blood pressure	<50 mmHg and decrease of >15 mmHg from baseline
	>105 mmHg and increase of >15 mmHg from baseline
Pulse	<50 bpm and decrease of > 15 bpm from baseline
	>120 bpm and increase of >15 bpm from baseline
Weight	>7% decrease, >7% increase

